6.1.3.2 Sensitivity analyses

Mean of multiple sleep latency test (MSLT) score is essentially a positive outcome. Thus, a supportive analysis will be performed using log transformed mean sleep latency scores. Log transformed mean sleep latency score data will be analysed using a mixed effect ANOVA model with treatment, actual treatment sequence, smoking status at screening, total sleep time at baseline treatment interaction with total sleep time at baseline and smoking status and period as fixed effects and subject as a random effect. Geometric means of each treatment and their ratio (LML134 vs placebo) along with 95% confidence intervals will be estimated using least square means by back transforming to the original scale.

A supportive analysis with may be performed with additional covariates (total sleep time on actigraphy during baseline, key PSG parameters at screening/baseline) that may potentially affect individual mean MSLT data.

6.1.3.3 Supportive Analysis

Primary analysis as mentioned in section 6.1.3 may be performed in a bayesian platform with non-informative priors for both LML and placebo.

Corporate Confidential Information
Corporate Confidential Information

6.2 Secondary objectives

6.2.1 Variables

The secondary variable is MSLT at each time point (1:30, 3:30, 5:30 and 7:30) separately, averaged over two consecutive test nights.

6.2.2 Descriptive analyses

MSLT

The secondary variable will be listed by treatment sequence, patient, period and time, and descriptive statistics will be provided, by treatment and time. Summary statistics will include mean (arithmetic and geometric), SD, CV (arithmetic and geometric), median, minimum, maximum.

An arithmetic mean +/- SD time profile (time-points: 1:30 AM, 3:30 AM, 5:30 AM, and 7:30 AM) plot will be provided for each treatment.

6.2.3 Statistical model, assumptions and hypotheses

MSLT

A mixed model repeated measure (MMRM) analysis of variance model, will be performed over mean sleep latency test (MSLT) scores with treatment, actual treatment sequence, period, time-point, and treatment*time-point as fixed effects. A saturated covariance structure will be used for observations coming from same subject. If an unstructured covariance cannot be fitted simpler covariance structures will be examined.

The overall treatment effect for LML134 vs placebo will be reported along with a 95% CI.

A line graph of means of MSLT with 95% CI over time may be provided .

A supportive analysis with may be performed with additional covariates (total sleep time on actigraphy during baseline, key PSG parameters at baseline/screening) that may potentially affect individual mean MSLT data.

6.2.3.1 Handling of missing values/censoring/discontinuations

Please refer section [6.1.3.1](#) .

Corporate Confidential Information

Corporate Confidential Information

7 Statistical methods for safety and tolerability data

All analysis will be performed under safety analysis set.

7.1 Variables

Adverse events, vital signs (blood pressure, pulse rate, body temperature), ECG intervals, laboratory measurements, AE and polysomnography (PSG) as well as subject demographics, baseline characteristics, and treatment information.

7.2 Descriptive analyses

Subject demographics and other baseline characteristics

All data for background and demographic variables will be listed by treatment and subject. Summary statistics will be provided for all subjects, as well as for each treatment.

Relevant medical history, current medical conditions, results of laboratory screens, drug tests and any other relevant information will be listed by treatment and subject.

Treatment

Data for study drug administration and concomitant therapies will be listed by treatment and subject.

Vital signs

All vital signs data will be listed by treatment, subject, and visit/time and if ranges are available abnormalities (and relevant orthostatic changes) will be flagged. Summary statistics will be provided by treatment and time.

Summary statistics of height, weight, temperature, blood pressure, and pulse rate will be provided by treatment and time using statistics like N, mean, median, standard deviation, and range.

ECG evaluations

All ECG data will be listed by treatment, subject and time, abnormalities will be flagged. Summary statistics will be provided by treatment and time.

Each ECG parameter will be summarized by treatment, time using statistics like N, mean, median, standard deviation, and range.

The same data will be plotted using arithmetic mean-SD graphs over time for each parameter separately. Separate lines will be drawn for each treatment in order to see any potential differences. Reference lines will be drawn for normal ranges (if available).

Clinical laboratory evaluations

All laboratory data will be listed by treatment, subject, and time and if normal ranges are available abnormalities will be flagged. A separate listing is provided presenting all parameters in a subject with any abnormal values. Summary statistics will be provided by treatment and time.

Adverse events

All information obtained on adverse events will be displayed by treatment and subject.

The number and percentage of subjects with adverse events will be tabulated by body system and preferred term with a breakdown by treatment.

Separate tables will be presented indicating event severity and study drug relationship.

An adverse event starting in one period and continuing into the next period is counted only in the onset period. A subject with multiple adverse events within a body system and treatment period is only counted once towards the total of this body system and treatment.

Polysomnography

Polysomnography data will be listed by treatment, subject and time. Summary statistics will be provided by treatment and time.

Other safety evaluations

Columbia suicide severity rating, alcohol test, drug test, cotinine test, pregnancy and assessment of fertility data will be listed by treatment and time.

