5. Action taken regarding investigational treatment.
All adverse events must be treated appropriately. Treatment may include one or more of the following:
 - no action taken (e.g. further observation only)
 - investigational treatment dosage increased/reduced
 - investigational treatment interrupted/withdrawn
 - concomitant medication or non-drug therapy given
 - hospitalization/prolonged hospitalization (see [Section 9.2](#) for definition of SAE)
6. its outcome (not recovered/not resolved; recovered/resolved; recovering/resolving, recovered/resolved with sequelae; fatal; or unknown).

Information about common side effects already known about the investigational drug can be found in the Investigator's Brochure (IB) or will be communicated between IB updates in the form of Investigator Notifications. Once an adverse event is detected, it must be followed until its resolution or until it is judged to be permanent, and assessment should be made at each visit (or more frequently, if necessary) of any changes in severity, the suspected relationship to the investigational drug, the interventions required to treat it, and the outcome.

The investigator must also instruct each subject to report any new adverse event (beyond the protocol observation period) that the subject, or the subject's personal physician, believes might reasonably be related to study treatment. This information must be recorded in the investigator's source documents; however, if the AE meets the criteria of an SAE, it must be reported to Novartis.

AEs will be collected in the CRF for subjects that fail screening.

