9.2 Serious adverse event reporting

9.2.1 Definition of SAE

An SAE is defined as any adverse event (appearance of (or worsening of any pre-existing) undesirable sign(s), symptom(s) or medical conditions(s)) which meets any one of the following criteria:

- is fatal or life-threatening
- results in persistent or significant disability/incapacity
- constitutes a congenital anomaly/birth defect
- requires inpatient hospitalization or prolongation of existing hospitalization, unless hospitalization is for:
 - routine treatment or monitoring of the studied indication, not associated with any deterioration in condition
 - elective or pre-planned treatment for a pre-existing condition (that is unrelated to the indication under study and has not worsened since the start of study drug
 - treatment on an emergency outpatient basis for an event not fulfilling any of the definitions of a SAE given above and not resulting in hospital admission
 - social reasons and respite care in the absence of any deterioration in the subject's general condition
- is medically significant, e.g. defined as an event that jeopardizes the subject or may require medical or surgical intervention.

All malignant neoplasms will be assessed as serious under "medically significant" if other seriousness criteria are not met.

Life-threatening in the context of a SAE refers to a reaction in which the subject was at risk of death at the time of the reaction; it does not refer to a reaction that hypothetically might have caused death if it were more severe (please refer to [ICH-E2D Guideline 2003](#)).

Medical and scientific judgment should be exercised in deciding whether other situations should be considered serious reactions, such as important medical events that might not be immediately life threatening or result in death or hospitalization but might jeopardize the subject or might require intervention to prevent one of the other outcomes listed above. Examples of such events are intensive treatment in an emergency room or at home for allergic bronchospasm, blood dyscrasias or convulsions that do not result in hospitalization or development of dependency or abuse (please refer to [ICH-E2D Guideline 2003](#)).

Any suspected transmission via a medicinal product of an infectious agent is also considered a serious adverse reaction.

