9.2.2 SAE reporting

Screen Failures

Note the following requirement for Screen Failures: SAEs occurring after the subject has provided informed consent until the time the subject is deemed a Screen Failure must be reported to Novartis.

Randomized Subjects

To ensure subject safety, every SAE, regardless of causality, occurring after the subject has provided informed consent and until 30 days after the last administration of study treatment must be reported to Novartis within 24 hours of learning of its occurrence as described below.

Any SAEs experienced after this period should only be reported to Novartis if the investigator suspects a causal relationship to study treatment.

All follow-up information for the SAE including information on complications, progression of the initial SAE and recurrent episodes must be reported as follow-up to the original episode within 24 hours of the investigator receiving the follow-up information. An SAE occurring at a different time interval or otherwise considered completely unrelated to a previously reported one must be reported separately as a new event.

Follow-up information provided must describe whether the event has resolved or continues, if and how it was treated, whether the blind was broken or not (if applicable) and whether the subject continued or withdrew from study participation. Each re-occurrence, complication, or progression of the original event must be reported as a follow-up to that event regardless of when it occurs.

If the SAE is not previously documented in the Investigator's Brochure or Package Insert (new occurrence) and is thought to be related to the study treatment a Chief Medical Office and Patient Safety (CMO & PS) Department associate may urgently require further information from the investigator for Health Authority reporting. Novartis may need to issue an Investigator Notification (IN) to inform all investigators involved in any study with the same study treatment that this SAE has been reported. Suspected Unexpected Serious Adverse Reactions (SUSARs) will be collected and reported to the competent authorities and relevant ethics committees in accordance with EU Guidance 2011/C 172/01 or as per national regulatory requirements in participating countries.

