An adverse event starting in one epoch and continuing into the next epoch is counted only in the onset period. A subject with multiple adverse events within a body system and treatment epoch is only counted once towards the total of this body system and treatment.

Other safety evaluations

All safety data will be listed by treatment, subject, and visit/time. Summary statistics for specific parameters will be reported based on clinical decision. Details of reporting will be mentioned in SAP.

Analysis of PSG data will be discussed in detail in SAP.

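### The onset-only AE counting rule has no exception for worsening, so an event already open at a later period's dosing that worsens there is not counted under the treatment on which it worsened

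*SAP*

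**What the plan says.** The SAP's AE table is a count of subjects: "The number and percentage of subjects with adverse events will be tabulated by body system and preferred term with a breakdown by treatment" (SAP 7.2). Two rules govern it. A subject is counted once per body system and treatment period, and "An adverse event starting in one period and continuing into the next period is counted only in the onset period". Protocol 11.5.2 has the same attribution rule in terms of epochs: "An adverse event starting in one epoch and continuing into the next epoch is counted only in the onset period". The glossary names screening as an example of an epoch, and protocol 3.1 also calls it a period.

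SAP 7.2 adds: "Separate tables will be presented indicating event severity and study drug relationship". It does not say whether the grade shown is the grade at onset, the worst grade, or the grade reached in each period. Neither document defines a treatment-emergent AE.

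On data capture, protocol 9.1 collects AEs from written consent and asks for a severity grade and a yes/no relationship for each event. It has the event followed to resolution, or until judged permanent, with assessment at each visit "of any changes in severity, the suspected relationship to the investigational drug, the interventions required to treat it, and the outcome". Under protocol 8.4, medical history and current conditions are collected up to the signing of consent.

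**The concern.** Onset-only attribution is sound for an event that simply carries on unchanged, because it prevents double counting. An event that worsens after a new dose is different: in someone who already has the symptom, worsening is how a drug effect would show itself. The rule treats the two cases alike.

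The safety objective is a comparison of LML134 with placebo, and these counts are the SAP's AE comparison. They would also feed the risk ratios with confidence intervals planned in protocol 11.5.2. A worsening left out of the treatment column where it occurred, or placed in the other column, alters that comparison. The chance for an event to be open at dosing is real. The assessment schedule runs screening and baseline from day -42 to day -1, AE collection starts at consent, and dosing is two nights per period.

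**Working it through.** The plan states no figure on this point, so the check is to apply the rule to the possible records.

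**Conditions for the problem to arise**

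1. The symptom starts after consent, so that it is an AE and not medical history (protocol 8.4, 9.1).
2. It is still open at the first dose of a later period. For a Period 1 event this means outlasting a wash-out of 1 to 5 weeks (protocol 3.3). For a screening event that is open at Period 1 dosing, no wash-out is involved.
3. Its severity increases after that dose.
4. The increase is recorded in the existing AE record, as the follow-up text in protocol 9.1 indicates.

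**Applying the rule when all four hold**

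| Onset | Where it worsens | Count under LML134 | Count under placebo |
|---|---|---|---|
| Screening | LML134 | 0 | 0 |
| Screening | Placebo | 0 | 0 |
| Placebo, Period 1 | LML134, Period 2 | 0 | 1 |
| LML134, Period 1 | Placebo, Period 2 | 1 | 0 |

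In every row the column for the treatment on which the worsening occurred shows 0. The first and third rows lower the LML134 count. The second and fourth lower the placebo count.

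**Severity table.** Take the third row with a mild event on placebo that becomes severe on LML134. If the record's worst grade is tabulated, a severe event appears under placebo. If the onset grade is tabulated, a mild event appears under placebo and the severe grade appears nowhere. The SAP does not choose between these. The case can arise only in placebo-first subjects, about half under the 1:1 allocation (protocol 6.2).

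**Scale per affected subject**

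- SAP 1.4 reports termination after 18 completers. Taking 18 as the LML134 denominator, one affected subject is 1/18 = 5.6 percentage points and two are 2/18 = 11.1.
- At the planned 36 evaluable subjects (protocol 11.7) the figures would be 1/36 = 2.8 and 2/36 = 5.6.
- The safety set includes anyone who received study drug, so the real denominator may exceed 18 and the shift per subject would then be smaller.

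The number of affected subjects cannot be derived: neither document gives AE rates, persistence through wash-out, or the chance of worsening.

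**The case against.** **Pre-existing insomnia.** Protocol 1.1 names insomnia both as a main symptom of SWD and as the major side effect of the drug class. A reader might infer that aggravated SWD insomnia would drop out of the LML134 count. The documents do not support that. Insomnia present before consent is medical history, so no AE record would be open for it. Its worsening after dosing would ordinarily be a new AE with onset in that period, and would be counted there.

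**Record-keeping.** A reader might infer that such a worsening is never counted. That depends on CRF practice. If sites enter it as a new AE, the rule counts it correctly. Protocol 9.1 points to one continuing record but gives no explicit entry rule, and the Site Operations Manual is not available. The SAE text does not settle it. Protocol 9.2.2 says "Each re-occurrence, complication, or progression of the original event must be reported as a follow-up to that event regardless of when it occurs", but the same section sends a serious event occurring at a different time interval to a separate report, and it covers only SAEs. The definition in protocol 9.2.1 includes "appearance of (or worsening of any pre-existing) undesirable sign(s), symptom(s) or medical conditions(s", but this is not tied to the counting rule.

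**Direction and size.** A reader might infer a bias toward no difference, or a given percentage loss in the risk difference. The rule is symmetric, so the direction holds only if LML134 aggravates open events more than placebo does. Any percentage would rest wholly on assumed rates.

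**Mitigation.** AE information is also displayed by treatment and subject, so individual cases can be reviewed in a study this small. Post-dose daytime sleep is measured by centrally scored PSG and summarised by treatment. The study is non-confirmatory and the SAP's AE tables are descriptive.

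All of this narrows the point and lowers its weight. None of it puts the worsening into the right column of the count.

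**Conclusion.** The concern holds in a limited form. For an AE that began after consent, is open at a later period's first dose, and worsens there within the same record, the stated rule leaves the worsening out of the count for the treatment on which it occurred. This follows from the text and is more than a missing detail. The appearance of the higher grade under placebo is only a possibility, because the grade rule is unstated.

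The expected effect is probably small: few AEs are likely to meet all four conditions, and Period 1 events must survive the wash-out. Each affected subject shifts the incidence by 5.6 percentage points if the denominator is 18. The conclusion assumes that sites follow the single-record approach suggested by protocol 9.1. It is worth correcting because the correction is cheap, not because a large distortion has been shown.

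**What to change.** Replace the carry-over sentence in SAP 7.2, before database lock, with a rule to this effect:

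- An AE that continues into the next period without an increase in severity is counted only in its onset period.
- An AE, including one with onset before first dose, whose severity increases after dosing in a later period is also counted in that period, at the severity and relationship recorded there.
- The onset period keeps the severity reached before that later dosing.

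This keeps the protection against double counting unchanged events and also settles which grade each period shows.

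Cost: a few SAP sentences and a check of AEs open at the first dose of either period. Such an event can then appear in both treatment columns, which a footnote should explain. Protocol 9.1 lists one grade and one relationship per event, so if the CRF does not hold dated changes, sites will have to be queried for the date and grade of the change and for the relationship in the later period. Answers given in retrospect carry some recall error, but the number of events should be small.

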3.3 Rationale for dose/regimen, route of administration and duration of treatment

Treatment duration

In each treatment period, subjects will receive the study drug on two consecutive nights. H3R inverse agonists, like LML134, rapidly increase histamine release in the brain after administration.

Corporate Confidential Information

It is therefore expected that a single dose of LML134 will have wakefulness promoting effects and a single administration of the drug would be enough to assess its efficacy. Clinical studies with other H3R inverse agonists have verified that a single dose of the compound can indeed promote wakefulness and prolong sleep latency ([Iannone et al 2010](#)).

The variability of MSLT sleep latency is large, particularly in multi-center studies. Therefore two nights of treatment are planned in the present study to allow calculation of mean sleep latency over the two-night period. The averaged readouts are expected to provide more robust results with lower variability than the single night readouts.

Treatment periods will be separated by a wash-out of 1-5 weeks, depending on each subject's night shift work schedule. Additionally, this washout period covers at least 5-times the half-life of LML134 (4.6 hours to 7.6 hours) to allow complete washout of LML134 from the body.

Dose of LML134 and time of administration

The dose of LML134 used in the present study is guided by results of the occupancy PET study and the PK/PD model based on the FIH study.

It is known from the literature ([Iannone et al 2010](#)) that at least 80% of RO is needed to reach full efficacy of H3R inverse agonists. SWD patients could benefit from the wakefulness promoting effect of LML134 during the hours that correspond to the night shift (from 22:00 to 6:00) and during the additional hours that cover the usual time of commute to home (from 6:00 to 8:00). It is, however, also important to minimize the impact of LML134 on daytime sleep (starting at about 10:00) following the simulated night shift. Therefore the selected dose of LML134 is expected to provide full wakefulness promoting effect for the entire duration of the simulated shift but also minimize effect on daytime sleep duration.

Corporate Confidential Information

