The main principle that guides selection of the LML134 dose is that RO should be sufficiently high to provide full efficacy during the entire simulated night shift. Therefore the dose of LML134 will be such that it is expected to provide >80% RO and thus full efficacy for about 10 hours post dose in 90% of the subjects. Corporate Confidential Information

Corporate Confidential Information

Thus study drug will be administered at approximately 22:00, at the beginning of the simulated night shift. Corporate Confidential Information

LML134 has a short half-life (4.6 hours to 7.6 hours). Corporate Confidential Information

Thus accumulation of LML134 exposure is not expected to lead to a further reduction in total sleep time compared to the first post-dose sleep period.

Corporate Confidential Information

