8.6.7 Polysomnography

PSG is the gold standard method to evaluate sleep. In the present study, PSG will be performed at Screening to exclude any other sleep disorder than SWD. Screening PSG will be scored locally at each site by personnel experienced in the procedure (such as sleep technologist and sleep specialist). PSG will also be performed during the daytime sleep following the first dose of LML134 in each treatment period to assess any effect of LML134 on sleep. Post dose PSG will be scored centrally.

Technical details of PSG are specified in the SOM.

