1.3.2. Secondary objective(s)

Secondary objective(s)	Endpoints related to secondary objective(s)

 To assess the safety and tolerability of LML134 compared to placebo in SWD patients 	
 Standard safety assessments such as vital signs, ECG, hematology, blood chemistry, urinalysis, AE reporting, and daytime PSG to assess drug effect on sleep

 To assess the plasma pharmacokinetics of LML134 in SWD patients 	
 Due to sparse sampling, only plasma concentrations will be listed and no PK parameter will be evaluated by noncompartmental analysis. The data will be part of the overall Population PK model

 To evaluate the time course of LML134 effect on wakefulness compared to placebo 	
 MSLT at each time point averaged over two consecutive test nights

[figure not shown]

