1.4 Study design and treatment

This is a randomized, subject and investigator-blinded, placebo controlled, crossover, multi-center Proof of Concept (PoC) study with in-house simulated laboratory night shifts in patients with SWD.

This non-confirmatory study will include two treatment arms: LML134 and placebo. The study will utilize a 2x2 crossover design, with two treatment periods and two sequences as shown in [Figure 1-1](#) whereas assessment details are shown in [Figure 1-2](#).

Approximately 46 subjects were planned to be randomized in this study (to achieve 36 completers). All subjects will receive both treatments (LML134 and placebo), one in each treatment period, with the order of treatment being randomized. The study is prematurely terminated based on business decision after 18 completers.

Figure 1-1 Study Design

2 First interpretable results (FIR)

No first interpretable result (FIR) is planned for this study. All the results will be represented in clinical study report (CSR).

4 Statistical methods: Analysis sets

For all analysis sets, subjects will be analysed according to the actual study treatment(s) received. This is due to fact that it is known that a few subjects has been mis-randomized to a different treatment group as compared to the planned list of randomization. In order to make use of full data , all analysis will be performed on actual treatment group received by subject instead of a planned one.

The full analysis set will include all subjects that received any study drug and had any post-baseline assessment.

The safety analysis set will include all subjects that received any study drug.

The PK analysis set will include all subjects with at least one available valid (i.e. not flagged for exclusion) PK concentration measurement, who received any study drug and with no protocol deviations that impact on PK data.

For subjects for which the actual treatment received does not match the randomized treatment the treatment actually received will be used for the analysis.

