7.3 Graphical presentation

Boxplots to visualize trends in longitudinal safety data (vitals, ECG, lab parameter, PSG) will be created.

ECG and vital signs data will also be plotted using arithmetic mean-SD graphs over time for each parameter separately. Separate lines will be drawn for each treatment in order to see any potential differences

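### Daytime PSG is an endpoint for the comparison with placebo, but the SAP plans no LML134–placebo difference and no confidence interval for it

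*SAP*

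**What the plan says.** SAP 1.3.2 and protocol 2.2 both list "daytime PSG to assess drug effect on sleep" among the endpoints of the secondary objective on safety and tolerability against placebo. Protocol 8.6.7 sets the timing: "PSG will also be performed during the daytime sleep following the first dose of LML134 in each treatment period". Protocol 3.1 puts that recording in the Day 2 recovery sleep, with about 8 hours in bed.

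Protocol 11.5.2 gives no method and passes the matter on: "Analysis of PSG data will be discussed in detail in SAP". The whole PSG entry in SAP 7.2 is "Polysomnography data will be listed by treatment, subject and time. Summary statistics will be provided by treatment and time", and SAP 7.3 adds "Boxplots to visualize trends in longitudinal safety data (vitals, ECG, lab parameter, PSG) will be created". The mean–SD plots in SAP 7.3 cover ECG and vital signs, not PSG. PSG appears elsewhere in the visible SAP only in the objectives, in the variable list of 7.1, and as a possible covariate in the supportive MSLT models (6.1.3.2 and 6.2.3).

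Both MSLT endpoints, by contrast, are given an LML134–placebo estimate with a 95% CI (SAP 6.1.3 and 6.2.3).

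**The concern.** The protocol does not treat sleep as a routine safety item. Section 1.1 calls insomnia the major side effect of H3R inverse agonists and says it limits their clinical use. Section 3.2 expects no clinically significant effect of LML134 on daytime sleep. Section 3.3 says the dose should "minimize effect on daytime sleep duration" and argues that "accumulation of LML134 exposure is not expected to lead to a further reduction in total sleep time compared to the first post-dose sleep period". Daytime PSG is the measurement that tests these expectations.

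Two treatment means without an interval cannot show which size of sleep loss the data rule out. The risk is greater because the trial stopped at 18 completers (SAP 1.4) instead of the planned 36. Similar means in a small sample can be read as no effect when they are only imprecise.

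Nor do the summary tables let a reader rebuild the comparison properly. By-treatment SDs carry no within-subject correlation. The safety set includes anyone who received any study drug, so subjects with one period only can enter one treatment mean and not the other. A raw subtraction of means is also not adjusted for period. SAP section 4 reports that "it is known that a few subjects has been mis-randomized to a different treatment group", so the actual sequences may be unbalanced. With no parameter named in advance, the choice among PSG variables also stays open.

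**Working it through.** The documents state no PSG standard deviation, correlation, margin or expected difference, and protocol 11.8 confirms that secondary variables were not powered. There is thus no plan figure to reproduce; Table 11-1 concerns MSLT only. The number of completers, 18, is from SAP 1.4. Every other input below is an assumption, shown over a range, including that all 18 have scorable PSG in both periods.

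**1. Precision of a crossover estimate, 9:9 split**

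The treatment estimate is half the difference between the two sequence means of the period difference. Its standard error is (SD_diff/2) × √(1/9 + 1/9) = SD_diff/√18, on 16 degrees of freedom.

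Half-width of the 95% CI = t(0.975; 16)/√18 × SD_diff = 2.120/4.243 × SD_diff = **0.50 × SD_diff**.

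| Assumed SD of within-subject difference | Half-width |
|---|---|
| 30 min | 15 min |
| 60 min | 30 min |
| 90 min | 45 min |

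**2. Comparison with what the summary tables allow**

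From by-treatment means and SDs alone, a reader can build only an unpaired interval: t(0.975; 34) × √(2/18) × SD = 2.032 × 0.333 × SD = 0.677 × SD.

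For the crossover interval, SD_diff = SD × √(2(1 − ρ)), where ρ is the within-subject correlation.

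| ρ | Crossover half-width | Against 0.677 × SD |
|---|---|---|
| 0 | 0.707 × SD | 4% wider |
| 0.3 | 0.591 × SD | 13% narrower |
| 0.5 | 0.500 × SD | 26% narrower |
| 0.7 | 0.387 × SD | 43% narrower |

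Break-even is where 0.707 × √(1 − ρ) = 0.677, that is, ρ of about 0.08. Below that, the lost degrees of freedom outweigh the pairing.

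**3. Period effect in the raw difference of means**

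Let n1 completers receive LML134 first and n2 receive placebo first, and let period 2 differ from period 1 by π. The LML134 mean then contains π × n2/18 and the placebo mean π × n1/18. The raw difference is off by π × (n2 − n1)/18.

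| Split (assumed) | Share of π carried | If π = 30 min (assumed) |
|---|---|---|
| 9:9 | 0 | 0 min |
| 11:7 | 4/18 = 22% | 6.7 min |
| 12:6 | 6/18 = 33% | 10 min |

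In the crossover estimate π adds equally to both sequence means of the period difference and cancels at any split.

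**The case against.** PSG is classed as safety data, and SAP section 7 handles vital signs, ECG, laboratory values and PSG in the same descriptive way. The trial is a non-confirmatory proof of concept. The objective states no hypothesis or margin, and side-by-side summaries are a comparison of a kind. The SAP contradicts no PSG method in the protocol, which promised only detail. The subject listings keep the pairing, so anyone can compute the 18 differences; what is lost is pre-specification and convenience rather than information. The sizes above rest on assumed SDs, correlations, sequence splits and a period effect, and a few mis-randomized subjects need not mean imbalance. The resulting interval may be too wide to settle anything.

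There is also redaction. Blocks are removed in SAP section 6, the last directly before section 7, and in the protocol after 11.5.5. PSG parameters are mentioned in section 6 as covariates, so a definition could sit in hidden text.

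Much of this stands as a limit on severity. No error rate and no primary conclusion is affected, and the period-bias figures are hypothetical. The redaction means absence can be asserted only of the visible text, although section 7, where PSG is assigned, shows no redaction. The core point survives: the promised detail amounts to two sentences and a boxplot, and leaving readers to derive the paired comparison from listings is not an analysis plan. A wide interval is itself the information that is missing, because it would stop similar means from being taken as evidence of no sleep loss.

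**Conclusion.** The concern holds. The visible SAP gives daytime PSG no named parameter, no LML134–placebo difference and no interval, although the endpoint serves a comparison with placebo and the crossover provides paired data. This is a gap in estimation and pre-specification that should be closed; it is not an error that undermines the trial.

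Its size depends on assumptions. With 18 evaluable pairs split 9:9, the interval would be about ±0.50 times the SD of the within-subject difference. It would be 13% to 43% narrower than an unpaired reading for correlations of 0.3 to 0.7, with no gain below about 0.08. The conclusion that an estimate is missing needs none of these figures. Confidence is medium because of the redacted text outside SAP section 7.

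**What to change.** In SAP 7.2:

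- Name PSG total sleep time on Day 2 of each period as the main PSG parameter. Sleep efficiency is optional, since time in bed is set at about 8 hours.
- Analyse total sleep time in a mixed model with treatment, period and actual sequence as fixed effects and subject as random.
- Report the LML134–placebo least-squares mean difference with its 95% CI, labelled as an estimate with no hypothesis test.
- State how many subjects contribute both periods.
- Keep the planned listings, summaries and boxplots.

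The cost is a few lines of SAP wording and one extra table. The post-dose PSG is already recorded and centrally scored (protocol 8.6.7 and 10.3), so no new data are needed. The interval may still be too wide to exclude a meaningful sleep loss; if so, the report should say that.
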